# **Data Analysis**

The semi-structured interviews and focus groups will be recorded and transcribed verbatim. Inductive thematic analysis will be used to analyse the data collected. Thematic analysis involves identifying and coding central themes within qualitative data through an iterative process (Braun and Clarke, 2006). Themes are conceptualised as ideas that reflect some level of meaning within the data (Jugder, 2016). The first step will involve descriptive coding of the data line by line, identifying words or phrases that capture salient components in the data. During the second step, interpretive codes will be synthesized from the descriptive codes. The interpretive codes will then be arranged into hierarchical categories, forming final overarching themes. (Tracy, 2013). The purpose of a process evaluation is to develop an understanding of the intervention, trial, context and mechanisms of change, therefore data analysis must be focused on answering these research questions (Grant et al., 2013). Themes will be identified at a semantic level, in that they will develop from the explicit content contained within the data. This is different to identifying themes at a latent level, which requires a more hermeneutic approach (Braun and Clarke, 2006). Semantic themes are appropriate for a process evaluation as the aim is to gather explicit information on the implementation of an intervention and trial processes (Forman et al., 2017).

Investigator triangulation will be used to ensure validity of the identified themes. This will involve regular review of the analysis and themes by the supervisory team to ensure that subjective bias is controlled for during the analysis of the data (Steinke, 2004). Method triangulation will also be used by comparing the quantitative data collected during phase two and comparing semi-structured interviews, focus groups and field notes (for example, comparing demographic or clinical data and recruitment rates with themes related to participation). Data source triangulation will also be used in the process evaluation. This involves collecting data from a variety of sources, and will be achieved by collecting information from a wide variety of participants, including participants from phase two, participants who declined to take part in the trial, and healthcare staff working on the unit (Carter *et al.*, 2014). The importance of objective oversight has been highlighted in the MRC guidance on process evaluations, due to potential bias that researchers involved in the development of an intervention may bring when evaluating its acceptability (Moore *et al.*, 2015).

# **Phase 4 – Economic evaluation**

# Data collection and management

Feasibility studies do not have the sample size required for the statistical power needed to establish effectiveness, therefore conducting a full cost-effectiveness evaluation within a feasibility study is not recommended (Hounsome and Shearer, 2015). However the feasibility of data collection methods and the appropriateness of outcome measures can be evaluated during a feasibility study to inform a full economic evaluation within a definitive randomised controlled trial.

Health and social care costs of participants will be collected using Patient Service Use Logs previously used in the Palliative Care in Chronic Kidney Disease study (PACKS) (Agus *et al.* (2017). These logs will collect information on health and social care service use during the intervention. The logs will be collected post-intervention and at six weeks and three months follow up. The outcome of interest will be the feasibility of using a Patient Service Use Log in a full economic evaluation according to proportion of participants who complete the Patient Service Use Log.

The EQ-5D-5L will be administered to patients in conjunction with the clinical outcome measures, pre/post-intervention and at 6 weeks and 3 months follow up. The EQ-5D-5L is recommended by NICE for deriving utility values for the calculation of quality adjusted life years in cost-effectiveness analysis within definitive economic evaluations (National Institute for Health and Care Excellence, 2012) and has been shown to be a valid measurement of health status in patients with ESKD (Cleemput *et al.*, 2004). However it is important to consider the burden of questionnaires on participants during a randomised controlled trial. The acceptability of administering the EQ-5D-5L to patients in conjunction with the KDQoL-SF 36 and the HADS will be explored by examining the completion rates and proportion of missing data for the EQ-5D-5L.

# Data analysis

A cost-consequence analysis is recommended by the National Institute of Health Research for both complex interventions and feasibility studies where the outcomes of interest are not clear (Hunter and Shearer, 2014). Costs and outcome measure data for both the intervention and control group will be presented using means and 95% confidence intervals in order to show a general overview of the economic costs of the intervention, and differences in resource use and outcome measures between groups. Completion rates and missing data for the Patient Service Use Log and the EQ-5D-5L will be presented as frequencies to assess the feasibility of data collection.

# **Progression Criteria**

Progression to a definitive RCT will be determined by recruitment rates and the acceptability of the intervention for patients and staff.

- 75-100% of the target sample size recruited will result in progression to a definitive RCT.
- 50-74% of the target sample size recruited will result in progression to a definitive trial after reviewing the protocol and data from the process evaluation, and making appropriate amendments to address barriers to recruitment.
- 25-49% of the target sample size recruited will result in progression to a definitive trial after reviewing the protocol with input from potential co-applicants to ensure that the protocol is modified to enhance recruitment rates.

- Less than 25% of the target sample size recruited will probably result in the trial not progressing, unless a significant modifiable barrier is identified within the process evaluation.
- Progression to a full trial will be contingent on the acceptability of the intervention for both patients and staff regardless of recruitment rates. This will be assessed within the qualitative process evaluation (Forman *et al.*, 2017). Any necessary modifications identified within the process evaluation to improve the intervention will be made prior to progression to a definitive trial.

The progression criteria for recruitment are the criteria used by the Northern Ireland Clinical Trials Unit (McConnell *et al.*, 2016), and were confirmed by contacting [name] via e-mail. The inclusion of a qualitative component within progression criteria is recommended by O'Cathain *et al.*, (2014) as qualitative research may be able to identify potential harms of an intervention that would not be captured within the quantitative results.

# **Ethical Considerations**

As the chief investigator is an academic of Queen's University Belfast, the University will sponsor this research and will be responsible for independent peer review of the study protocol. This research falls under Category B research in the University regulations for research involving human participants from within a healthcare trust (Queen's University Belfast, 2013), therefore the application for ethical approval will be made to the Office of Research Ethics Committees Northern Ireland (ORECNI), through the Integrated Research Application System (IRAS). The local collaborator on site will be the consultant nephrologist [name].

# Informed Consent

To ensure informed consent is obtained freely from participants they will initially be approached by the gatekeeper on site, who will provide them with a verbal summary of the project and the participant information sheet. This will ensure that participants feel free to decline to participate by removing the power dynamic that may be present in a direct approach from the researcher. The participant information sheet (Appendix 1, Appendix 3, Appendix 5) will contain information on the purpose and process of the research, how data will be collected, stored, and used, their ability to withdraw from the study at any time, the

right to refuse to answer questions during the interviews, a guarantee of anonymity and how this will be maintained, the expectations of participants, including time commitments and any potential risks or difficulties that could arise during the research (Connolly, 2003). Contact details for the researcher will be provided should the participant have any questions. The patient will be given time to consider participation over 48 hours, before finally being approached by the researcher with a formal consent form.

# Confidentiality and Anonymity

Participants will be allocated codes for the purpose of data collection for the feasibility randomised controlled trial. All data will be stored in accordance with the Data Protection Act (2018). All identifiable information will be confidential and stored in a locked filing cabinet in a locked room at Queen's University Belfast School of Nursing and Midwifery. For the process evaluation pseudonyms will be allocated to participants during transcription (Allmark *et al.*, 2009). Data will be stored for a minimum of 5 years and subsequently destroyed. The data recorded on all audio recording devices will be erased once it has been transcribed and stored on a secure, encrypted computer. As focus groups will be used for data collection during the process evaluation, the importance of confidentiality will be reiterated prior to the commencement of each group. During the process evaluation, participants will be provided with limitations of confidentiality and anonymity on information sheets prior to commencement of the study. Participants will be informed that if the interview or focus group provides evidence for serious concerns regarding child welfare, the safety of the participant or the safety of others, that a third party will have to be informed.

# Welfare of Participants

The research involves participants who have an advanced illness. During the feasibility randomised controlled trial participants will be receiving an arts-based intervention whilst also receiving haemodialysis. Due to the importance of maintaining vascular access and not inhibiting the work of healthcare professionals, the intervention will be designed with input from healthcare professionals working in this clinical setting, as well as artists from Arts Care Northern Ireland who have experience adapting arts-based interventions to the clinical environment. The process evaluation will also occur in parallel to the implementation of the intervention, ensuring that any issues with the intervention are identified and can be addressed during the trial (Moore *et al.*, 2014).

As the questionnaires participants fill out explore subjects such as quality of life and mental health, and the interviews and focus groups may broach sensitive subjects relating to the experiences of living with ESKD or the experiences of working with patients who have an end-stage illness, there is a potential for participants to experience emotional distress. A distress protocol (Appendix 7, Appendix 8) will be in place to address these issues (Haigh and Witham, 2015) and participants will be provided with information regarding relevant supportive services available. Participants will be reminded they can stop the interview at any time, they are not obligated to answer questions they feel are too sensitive, or provide information they are not comfortable sharing. A renal counsellor will also be present on the advisory group and will provide guidance on maintaining the emotional wellbeing of participants. Two additional distress protocols have also been developed for the potential that a participant discloses suicidal thoughts (Appendix 9) or achieves a score on the Hospital Anxiety and Depression Scale that suggests the presence of a clinical mental health condition (Appendix 10).

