When exploring the staff perceptions of arts-based interventions, the focus in the literature is on how the intervention impacts the patients, with fewer studies examining the effect of the intervention on healthcare staff themselves (Bungay et al., 2014; Boyce et al., 2017). It is particularly important to consider the potential positive and negative effects of arts-based interventions on healthcare staff, due to the unique nature of the clinical working environment. A critical review by Wilson et al., (2015) explored healthcare staff perceptions of arts-based interventions and identified numerous benefits of arts-based interventions including reductions in stress and improved working relationships. However the potential negative outcomes included interference with work flow, increased stress and restricted communication between healthcare staff. Any negative impact on the ability of healthcare staff to perform their job could have significant consequences for patient safety; therefore the acceptability of an intervention for healthcare staff is important to consider (May, 2013). The acceptability for patients must also be taken into consideration. If an effective intervention is burdensome or non-engaging, patients will not participate and not experience the benefits (May, 2013). In order to evaluate whether an intervention is acceptable in practice, a process evaluation must be conducted. Process evaluations provide a detailed understanding of complex interventions by examining their implementation, mechanism of impact and context (Moore *et al.*, 2015).

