# Randomisation

The proportion of eligible participants willing to be randomised will be collected through the use of screening logs (Lancaster *et al.*, 2004). Participants will be randomly allocated to a control group or experimental group following the collection of baseline data. Block randomisation at a ratio of 1:1 will be used to ensure both groups comprise the same number of participants (Suresh, 2011). Patients will be randomly allocated according to the days of the week they attend the unit for haemodialysis, as opposed to at an individual level. As the renal unit is an open environment allocation according to shift pattern will reduce the risk of participants within the control group viewing implementation of the intervention, which would introduce potential contamination (Mc Daid *et al.*, 2006). Sealed envelopes will contain the allocation and these will be stored in a locked filing cabinet on site, and will be opened once consent and baseline data have been obtained. Participants who are randomly allocated to the control group will be instructed not to participate in any art activities during

their haemodialysis sessions throughout the study, but that once data collection is completed they will be provided with art supplies and participate in a facilitated session.

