# **Data Collection and Management**

Approximately 13 patients will be recruited into the process evaluation. Simulations have shown that this sample size of 10 should identify 80% of problems within a complex intervention (O'Cathain et al., 2014), while data saturation is likely to be reached at 12 interviews on average (Guest et al., 2006). The principle of 10 + 3 for data saturation outlines that a minimum of 10 interviews should be conducted, followed by at least 3 consecutive interviews that present no new findings (Francis et al., 2010), therefore a sample of 13 patients will be recruited for semi-structured interviews. Approximately 5 healthcare staff will be recruited into each focus group, with a proposed total of 3 focus groups (Schneider et al., 2009). The dialysis unit in which the study is taking place is relatively small, therefore the focus groups will be limited by the amount of staff available who meet the eligibility criteria and the requirement to produce a manageable amount of data for the time limitations of the study (Carlsen and Glenton, 2011; O'Cathain et al., 2014). However, these are approximate sample sizes, and data collection will continue until data saturation is reached. The researcher will provide the participants with a consent form prior to commencement of the focus group (Appendix 6). Data saturation will be determined when there is no new data being found from which additional themes can be developed (Guest et al., 2006).

Data collection for the process evaluation will occur in parallel to the feasibility randomised controlled trial, during implementation of the intervention and follow up (Moore *et al.*, 2014). The semi-structured interviews will be conducted with patients in their own home to maintain

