3.1 Management of data sets

Data will be collected and analysed by the PhD student responsible for this study, with oversight and supervision from the PhD supervisory team and guidance from a University Statistician. Quantitative data will be analysed using Statistical Package for the Social Sciences (SPSS v 24), while qualitative data for the process evaluation will be digitally recorded and transcribed verbatim prior to data analysis. All data will be stored in accordance with the Data Protection Act (2018) participants will be provided an anonymous code and identifiable information will be removed from the qualitative data to maintain confidentiality. A more detailed overview of data storage and management is included in the study protocol, and an overview of the timing of data collection can be seen in Table 1.

| Table 1 | Screening Baseline | Post intervention/ 3 weeks | 6 weeks | 3 months (12 weeks) |
|---|---------------------------|----------------------------------|---------|------------------------|
| PATIENT | | | | |
| Informed Consent | Х | | | |
| Inclusion/Exclusion Criteria | X | | | |
| Demographic Data | Х | | | |
| 9-point Clinical Frailty Scale | x | | | |
| KDQOL-SF36 | x | x | X | X |
| EQ-5D-5L | X | X | X | X |
| HADS | x | x | X | x |
| Patient Service Use Log | x | X | X | x |
| Diabetes and diabetic comorbidity check | x | X | X | x |
| Qualitative interview | At one point during study | | | |
| HEALTHCARE PROFESSIONALS | | | | |
| Informed Consent | X | | | |
| Inclusion/Exclusion Criteria | x | | | |
| Qualitative interview | At one point during study | | | |

4 Sample Size Calculation

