4.1 Sample size for feasibility RCT and economic evaluation

A sample size of 30 is recommended by the NIHR's Research Design Service for the estimation of a parameter, such as sample size, recruitment or attrition rate, for a definitive randomised controlled trial, although they recognise that advice varies from 24 to 50 participants. Due to the increased risk of identifying a statistically significant result with larger sample sizes, and practical limitations of a small, single centre study, a sample size of 30 was selected for the feasibility RCT. A university statistician was consulted who confirmed that a sample of 30 was an appropriate sample size to meet the objectives of the study. A more comprehensive overview of the sample size decision is available in the study protocol.

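### The process evaluation cannot ensure that any intervention problem is found and addressed during the trial, and no intervention-related harm is defined, recorded and reported by arm for all participants

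*Protocol*

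**What the plan says.** The Protocol's Welfare of Participants section names two physical concerns, protecting vascular access and not hindering staff at work, and says the intervention will be designed with unit staff and experienced artists for that reason. It then describes the process evaluation, run alongside delivery, as "ensuring that any issues with the intervention are identified and can be addressed during the trial". The Background gives the reason for concern about staff: "Any negative impact on the ability of healthcare staff to perform their job could have significant consequences for patient safety".

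Phase 3, Data Collection and Management, gives the size: "Approximately 13 patients will be recruited into the process evaluation", approximate and continuing to saturation, plus about three focus groups of about five staff. It lets collection run through both delivery and follow-up. Phase 3, Recruitment, makes patient interviews voluntary. Phase 3, Data Analysis, adds field notes and people who declined the trial. SAP Table 1 schedules the qualitative contact "At one point during study", for patients and staff alike, and equates post-intervention with 3 weeks in a 12-week schedule.

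The Progression Criteria make acceptability a condition of progressing whatever the recruitment rate. They assess it in the qualitative work, because that may reveal "potential harms of an intervention that would not be captured within the quantitative results". They place modifications before the definitive trial.

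**The concern.** The safeguard is worded as a guarantee: any issue, identified, and addressable in time. A guarantee needs a route that reaches every participant, soon enough to act, with a defined way of acting. A single voluntary interview with under half the sample, possibly weeks after delivery has stopped, is not that route.

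The structured data do not fill the gap. If a needle or line problem, a shortened dialysis session or an abandoned art session is dealt with on the unit, nothing in the SAP turns it into a count. The acceptability decision, which overrides recruitment, could then be taken without knowing how often such events occurred. There would also be no control-arm count to set beside the intervention arm, although access problems can arise without any art activity.

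**Working it through.** **Inputs.** Trial size: "a sample size of 30 was selected for the feasibility RCT" (SAP 4.1). Allocation: "Block randomisation at a ratio of 1:1 will be used" (Protocol, Randomisation), so 30/2 = 15 intervention patients. That is an assumption, since allocation follows dialysis days. Patients interviewed: about 13 (Protocol, Phase 3).

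**1. The plan's own sample figure.** The rule is "a minimum of 10 interviews should be conducted, followed by at least 3 consecutive interviews that present no new findings". 10 + 3 = 13, so the figure reproduces.

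**2. The plan's own detection figure.** Phase 3 credits 10 interviews with 80% of problems. This cannot be reproduced, because no per-interview detection probability is given. It can be inverted if every problem is assumed equally detectable: 1 − (1 − p)^10 = 0.80 gives p = 1 − 0.20^(1/10) = 0.149. At 13 interviews, 1 − (1 − 0.149)^13 = 0.88. About 12% of problems would remain unfound on the document's own basis.

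**3. Chance that the interviews miss an issue affecting k patients.** With m interviewed out of N, P(miss) = C(N − k, m)/C(N, m).

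| Interviewed | k = 1 | k = 2 | k = 3 |
|---|---|---|---|
| 13 at random from 30 | 17/30 = 57% | (17×16)/(30×29) = 31% | (17×16×15)/(30×29×28) = 17% |
| 7 of the 15 intervention patients | 8/15 = 53% | (8×7)/(15×14) = 27% | (8×7×6)/(15×14×13) = 12% |
| 13 of the 15 intervention patients | 2/15 = 13% | (2×1)/(15×14) = 1% | 0% |

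Phase 3 admits any patient recruited into Phase 2, so control patients may be interviewed. No arm split is given, and nothing secures the last row. The table assumes that selection is unrelated to the issue, that the interview comes after it, and that an affected interviewee reports it.

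**4. Timing and action.** Delivery ends at about week 3, and the single interview may fall anywhere up to week 12. An issue first heard after week 3 is too late for that participant. The Welfare section speaks of acting during this trial; the Progression Criteria speak of acting before the next one. No section says how an issue raised mid-trial leads to a change.

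**5. What is recorded for everyone.** SAP 2.1, 2.2, Table 1 and 6.1 to 6.4 were read for harm items. Present: HADS, KDQOL-SF36, EQ-5D-5L, a diabetes check, service use including A&E visits and admissions, and reasons for withdrawal. Absent: an access problem during a session, dialysis interrupted or shortened, an art session stopped, and a distress-protocol activation.

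**6. What asking everyone would add.** A harm caused by the art sessions arises only in the intervention arm, so n = 15 is the relevant number. With an assumed event rate r and independent patients, the chance of at least one case among those asked is 1 − (1 − r)^n.

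| Assumed rate | n = 7 | n = 13 | n = 15 |
|---|---|---|---|
| 10% | 52% | 75% | 79% |
| 5% | 30% | 49% | 54% |

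The detection gain is large if 7 intervention patients are interviewed and small if 13 are. In either case the checklist also gives a complete count for both arms at fixed times.

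**The case against.** The case on the other side is substantial. A reader might infer that the interviews are the only way a problem could surface and that nothing about harm is known for patients who are not interviewed. The documents do not support that:

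- Appendix 7 covers Phase 2 as well as Phase 3.
- HADS goes to all participants at baseline and weeks 3, 6 and 12. Appendix 10 sets a response at a score of 12 or more, and Appendix 9 covers suicide risk.
- SAP 6.4 logs A&E visits and admissions for everyone.
- About 5 × 3 = 15 staff are to be heard, and they are well placed to see access problems and disrupted work.
- Design with unit staff is itself a preventive measure.

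A reader might also infer that problems behind withdrawals would go uncounted. SAP 6.1 contradicts this, since it records the reasons and puts them in the flow diagram.

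A third tempting step is 13/30 × 3/12 = 11% as the chance that a one-patient problem is heard in time. It assumes interviews spread evenly over 12 weeks, which no section states. It also ignores that, if enrolment is staggered (also not stated), later patients could benefit from earlier reports.

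These points limit the concern without removing it. Staff too are scheduled for one contact, field notes appear only as a means of triangulation, decliners did not receive the intervention, and saturation concerns themes, not event counts. None of the all-participant items is designated as a harm or captures an event managed on the unit, and the distress appendices prescribe responses without any tally.

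It is also fair that counts by arm will be imprecise with about 15 per arm, and confounded with dialysis day. That rules out a test but not a descriptive report.

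**Conclusion.** The concern holds in a limited form. The claim that the process evaluation ensures any issue is found and can be addressed during the trial goes beyond the design: beyond the 80% figure the Protocol cites, beyond what one interview possibly held after week 3 can do, and against the Progression Criteria on when changes are made. Separately, the supplied text does not prospectively define, record and report any intervention-related harm for all participants by arm.

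If the interviews stood alone, an issue affecting one patient would be missed between 13% and 57% of the time, depending on an arm split the documents leave open. These figures rest on 15 intervention patients, selection unrelated to harm, and full reporting. Staff and the other sources would lower the overall miss rate by an amount that cannot be calculated. A preference for interviews among satisfied patients would raise the miss rate.

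This should be corrected because it is cheap and informs the acceptability decision. It does not show that the trial is unsafe. Information sheets and consent pages were not available, and nothing is inferred from them.

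**What to change.** - Add one row to SAP Table 1 at weeks 3, 6 and 12, for all participants in both arms: a short fixed checklist of vascular-access problem during a session, dialysis interrupted or shortened, art session stopped and why, and distress-protocol activation.
- Have stopped art sessions noted on the day, so that the weeks of delivery do not depend on recall.
- In SAP section 6, report the counts by arm descriptively, without a test, noting that numbers are small and allocation follows dialysis days.
- In the Progression Criteria, state that these counts are considered alongside the qualitative data when acceptability is judged.
- Reword the Welfare of Participants sentence so that it says the process evaluation may help to identify issues, and reconcile it with the Progression Criteria on when issues are acted upon.
- State how interviewees are expected to divide between the arms.

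The cost is a few minutes at visits already scheduled, a one-page form and a minor amendment, with no extra patients. Checking the answers against the unit's session records would strengthen them but needs added record access, so it is best left optional.
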